4. STUDY PLAN

4.1. Study Design

This is a Phase 2, randomized, double-blind, placebo-controlled, multicenter clinical trial to evaluate the antiviral effects, immunogenicity, and safety of HepTcell in treatment-naïve patients with inactive CHB and low HBsAg levels (10 to 200 IU/mL).

After providing written informed consent, patients will undergo a screening period of up to 35 days. A Fibroscan will be performed in all patients who have not had this examination within the previous 12 months before Screening with the exception of patients with a prior history of liver biopsy within the past 2 years demonstrating no evidence of significant fibrosis.

Patients who meet inclusion and exclusion criteria will be randomized in a 1:1 ratio to receive 6 IM doses of HepTcell or placebo (normal saline) at study visits 4 weeks apart (Days 1, 29, 57, 85, 113, 141). Randomization may occur up to 3 working days before the first day of dosing to allow for the possible preparation of study medication by a central pharmacy and shipment to the study site. Adverse events (AEs) will be monitored, and blood samples will be collected for qHBsAg, anti-HBs, HBV DNA, HBV pg-RNA, HBcrAg, and IFN-γ ELISpot assay in PBMCs. Patients will record any reactogenicity events (see Appendix 1) for 7 days after each administration of study medication in a diary. A visit consisting of a targeted physical examination and safety laboratory tests, including liver panels, will be conducted 7±2 days after administration of Doses 1 and 2 of study medication. These visits, per the Schedule of Events (Table 1 and Table 2), may be conducted at home or workplace or, in part, as a telemedicine visit, at the discretion of the Investigator.

If the patient has experienced an acute illness or temperature > 38°C in the 2 days prior to dosing, the administration of study medication and corresponding visit will be delayed until the illness or fever has resolved.

A Safety Committee will conduct regular blinded reviews of all AEs and reactogenicity events. The safety of study participants will also be overseen by an unblinded Data Monitoring Committee (DMC); its responsibilities will be laid out in a DMC charter.

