A sentinel cohort of 12 patients (6 receiving HepTcell and 6 placebo) will undergo blinded safety review by the Safety Committee 7 to 10 days after all ongoing patients in the sentinel cohort have completed the respective dose of study medication and will determine the decision to continue at that dose to the expanded cohort. Safety will be assessed in the sentinel cohort before each dose is administered to the expanded cohort. If any of the Stopping Rules in Section 7.1.1 are met in one or more patients and the event(s) is deemed possibly or probably related to HepTcell, dosing will be suspended pending DMC review. DMC recommendations may include instituting modifications to ensure the safety of continued dosing or discontinuing the study. If none of the Stopping Rules are met, randomization and dosing may continue in the expanded study cohort. Patients will be unblinded as necessary to assess the relationship between the study medication and events that meet criteria for Stopping Rules.

Safety laboratory testing (Table 3), including liver panel, for Doses 1 and 2 will be obtained during the visits conducted 7±2 days after these doses of study medication. Safety laboratory testing following Doses 3, 4 and 5 will be obtained in the interval from 7 days after dose administration and before the next dose of study medication is administered. Safety labs after Dose 6 will be assessed at the Day 169 visit. Investigators will review the eligibility of all patients prior to dosing to determine if the next treatment is to be administered. Eligibility for the next treatment will include: 1) confirmation that patients did not meet a Stopping Rule (Section 7.1.1); 2) confirmation that the pre-treatment liver parameters are within acceptable ranges for treatment (below); 3) confirmation that patients do not have a new confirmed or suspected IMC (Appendix 2). Patients not meeting these criteria will not be treated.

If abnormalities of ALT, AST, total bilirubin, direct bilirubin, or international normalized ratio (INR) are reported after dosing is commenced, the following monitoring and dosing rules will be applied:

Toxicity	Management	Discontinuation of Study Medication
ALT or AST \geq 5×but < 10 × ULN, and Total and direct bili < 1.5×ULN, and INR < 1.3 ×ULN	Continue dosing Monitor liver panel weekly If ALT/AST fall to <1.5×ULN, stop weekly monitoring	

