4.3. Rationale for Study Design

The study design replicates the general design of the prior Phase 1 study but extends treatment from 3 to 6 doses and the follow-up after the last dose of study medication from 30 to 52 weeks. These modifications will enhance the effects of study medication and provide a more extended follow-up to assess the durability of immunogenicity and AEs. Diaries will be collected for reactogenicity events at visits on Days 8 and 36, which correspond to 7±2 days after the first and second dose of study medication. A visit consisting of a targeted physical examination will be conducted 7±2 days after administration of Doses 1 and 2 of study medication. Safety laboratory testing (Table 3), including liver panel, for Doses 1 and 2 will be obtained during the visits conducted 7±2 after these doses of study medication. Safety laboratory for Doses 3, 4 and 5 will be obtained in the pre-treatment interval from 7 days after dose administration through the time that the next dose of study medication is administered. Safety labs after Dose 6 will be assessed at the Day 169 visit. Investigators will review the eligibility of all patients prior to dosing to determine if the next treatment is to be administered. Eligibility for the next treatment will include: 1) confirmation that patients did not meet a Stopping Rule (Section 7.1.1); 2) confirmation that the pre-treatment liver parameters are within acceptable ranges for treatment (Section 4.1); 3) confirmation that patients do not have a new confirmed or suspected IMC (Appendix 2). If abnormalities of ALT, AST, total bilirubin, direct bilirubin, or INR are reported after dosing is commenced, the monitoring and dosing rules of Section 4.1 will be applied. These procedures are considered sufficient to evaluate reactogenicity events, particularly after Doses 1 and 2, and guard

against hepatitis flares and liver function abnormalities that would preclude the scheduled administration of the next dose of study medication.

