- 1 If an authorized COVID-19 vaccine has been administered in proximity to a scheduled IP administration, a ± 3 day window is allowed for IP dosing.
- ^m After Day 169 or ET, only MAEs, NCIs and IMCs will be recorded.
- ⁿ A single blood sample will be collected for biobanking at the beginning of the study (prior to dosing on Day 1) and end of the study. This sample will be used for future analyses not specified in the protocol. Analysis will be limited to HBV serologic and HBV-specific DNA and RNA and patients' DNA will not be analyzed.
- ° Safety laboratory testing, including liver panel, for Doses 1 and 2 will be obtained during the visits conducted 7±2 days after these doses of study medication. Safety laboratory testing following Doses 3, 4 and 5 will be obtained in the interval from 7 days after dose administration and before the next dose of study medication is administered. Safety labs after Dose 6 will be assessed at the Day 169 visit.
- ^p Diaries will also be reviewed at the Day 85, Day 113, Day 141 and Day 169 visits

Table 2 Schedule of Events – Follow-up Period

	Follow-Up Period					
Study Visit	Day 232	Day 323	Day 414	Day 505 or ET ^a		
Completion of Week (number)	33	46	59	72		
Window (days)	±10 days	±10 days	±10 days	±10 days		
Visit may be conducted at home or work or in part as a telemedicine visit ^b	X		X			
Immunosuppressive medications, vaccines, and new HBV treatments (only) ^c	X	X	X	X		
Targeted and symptom-driven PE	X	X	X	X		
Height and weight				X		
Vital signs ^d	X	X	X	X		
ECG ^d				X		
Hematology and serum chemistry	X	X	X	X		
Liver panel	X	X	X	X		
HBV serology and viral markers ^e		X		X		
Whole blood for PBMC isolation		X		X		
MAEs, NCIs and IMCs (only) ^f	X	X	X	X		

AE = adverse event; ECG = electrocardiogram; ET = early termination; HBV = hepatitis B virus; HIV = human immunodeficiency virus; MAE = medically-attended adverse event; NCI = new-onset chronic illness; IMC = immune-mediated medical condition; PBMC = peripheral blood nonnuclear cell; PE = physical examination.

^a If a patient prematurely discontinues study medication before Day 505, Day 505/Early termination procedures will be performed.

^b A telemedicine visit would include a home visit by appropriate trained personnel to perform a target and symptom-driven physical and obtain vital signs and safety laboratories. The remaining portions of the visit may be conducted virtually by the study investigator.

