6.4. Dosing Modifications

The sentinel cohort of 12 patients will undergo blinded safety review by the Safety Committee 7 to 10 days after all ongoing patients in the sentinel cohort have completed

the respective dose of study medication and will determine the decision to continue at that dose into the expanded cohort. Safety will be assessed in the sentinel cohort before each dose is administered to the expanded cohort. If any of the Stopping Rules in Section 7.1.1 are met in one or more patients in the sentinel cohort and the event(s) is deemed possibly or probably related to HepTcell, dosing will be suspended pending DMC review. DMC recommendations may include instituting modifications to ensure the safety of continued dosing or discontinuing the study. If none of the Stopping Rules (below) are met, randomization and dosing may continue in the expanded study cohort. Patients will be unblinded as necessary to assess the relationship between the study medication and events that meet criteria for Stopping Rules. Patients who experience events that meet criteria for Stopping Rules will permanently terminate dosing.

Monitoring and dosing rules for patients who experience liver abnormalities is described in Section 4.1.

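### The 7-10 day sentinel review can release Doses 3-6 to the expanded cohort before all sentinel labs and diaries for that dose are in

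*Protocol*

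**What the plan says.** - **Review and release.** Protocol 4.1 places the blinded sentinel review "7 to 10 days after all ongoing patients in the sentinel cohort have completed the respective dose of study medication". That review decides whether the dose goes to the expanded cohort. Protocol 6.4 applies it to every dose: "Safety will be assessed in the sentinel cohort before each dose is administered to the expanded cohort".
- **Doses 1 and 2.** A visit with safety labs "will be conducted 7±2 days after administration of Doses 1 and 2 of study medication". Diaries are collected at the same visits (Protocol 4.3).
- **Doses 3-5, labs.** "Safety laboratory testing following Doses 3, 4 and 5 will be obtained in the interval from 7 days after dose administration", with the next dose as the latest time.
- **Dose 6, labs.** "Safety labs after Dose 6 will be assessed at the Day 169 visit".
- **Doses 3-6, diaries.** Table 1, footnote p: "Diaries will also be reviewed at the Day 85, Day 113, Day 141 and Day 169 visits". Table 1 has no visit between Days 57, 85, 113, 141 and 169.
- **Stopping Rules (Protocol 7.1.1).** One related event in one sentinel patient suspends dosing pending DMC review.
- **Rationale (Protocol 4.3).** The lab and diary schedule is considered sufficient to evaluate reactogenicity and to guard "against hepatitis flares and liver function abnormalities that would preclude the scheduled administration of the next dose of study medication".
- **Earlier schedule.** SAP 5.3.3.9 and 5.3.3.11 say that visits on Days 64, 92, 120 and 148 were removed, and that some patients followed previous protocol versions.

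**The concern.** A sentinel cohort protects later patients only if its data are seen before those patients are dosed. The review time suits a schedule with a visit one week after each dose, and the current schedule has that only for Doses 1 and 2. From Dose 3 on, the committee can meet on time and release the dose while the labs or diaries of the most recently dosed sentinel patients are not yet due.

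Five Stopping Rules apply to any one patient: ALT/AST, INR, bilirubin (total, or direct in Gilbert Syndrome), SAE, and severe systemic reactogenicity. Three rest on labs and one on the diary, so only the SAE rule is independent of the data that may be missing. Protocol 8.3.1 keeps reactogenicity apart from AEs unless it is serious, so a severe but non-serious reaction could sit in the diary until the next visit.

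The rationale in 4.3 is framed around a patient's own next dose and does not address release to other patients. It also says that "The study design replicates the general design of the prior Phase 1 study but extends treatment from 3 to 6 doses", so the prior study did not cover Doses 4-6.

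**Working it through.** The plan gives no figure on this point, so the check compares scheduled days and then sizes the gap.

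**1. Gap for the last-dosed sentinel patient.** Dose days are from Protocol 6.3 and visit days from Table 1. The review falls at dose day + 7 to + 10.

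| Dose | Dose day | Review | Next visit | Gap (days) |
|---|---|---|---|---|
| 3 | 57 | 64-67 | 85 | 18-21 |
| 4 | 85 | 92-95 | 113 | 18-21 |
| 5 | 113 | 120-123 | 141 | 18-21 |
| 6 | 141 | 148-151 | 169 | 18-21 |

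With ±2 days on both dose and visit, the next visit is 24 to 32 days after the dose, so the gap is at least 24 - 10 = 14 days. This is certain from the schedule for Dose 3-6 diary review and Dose 6 labs. For Dose 3-5 labs it is an upper range, because the window opens at day 7. For Doses 1-2 the visit falls at days 5-9 and the review at days 7-10, so the two overlap by 2 days at most.

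**2. When it matters.** If an expanded patient starts L days after the last sentinel patient's Dose 1, each of that patient's doses falls L days after the matching sentinel dose, while the sentinel's next visit falls 28 days after it. Any L below 28 puts the expanded dose first. At L = 8, expanded Dose 3 falls on sentinel Day 57 + 8 = 65; at L = 21, on Day 78. Both precede Day 85. No minimum L is stated beyond the review itself.

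**3. Sentinel patients outstanding.** Assume even accrual, which the documents do not give: 80 patients over 24 months (Protocol 5.1) is 80/730 = 0.110 per day, or one per 9.125 days. Sentinel patient i is 7 to 10 + (12 - i) × 9.125 days past the dose at review and needs 28.
- Review at day 7: 12 - i ≥ 21/9.125 = 2.30, so 9 complete and 3 outstanding.
- Review at day 10: 12 - i ≥ 18/9.125 = 1.97, so 10 complete and 2 outstanding.

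**4. Expanded patients who could be dosed in the gap.** 18 × 0.110 = 2.0 to 21 × 0.110 = 2.3, about half of them (1.0-1.2) on HepTcell.

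**5. Sensitivity.** At three times that rate (one per 3.04 days, an arbitrary multiple), 21/3.04 = 6.90 and 18/3.04 = 5.92. That leaves 6-7 of 12 outstanding and 5.9-6.9 expanded patients dosed, 3.0-3.5 of them on HepTcell.

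**The case against.** The strongest reply is that the gap may never have touched a sentinel patient. The sentinels are the first 12 patients, and the removed visits (Days 64, 92, 120, 148) fall exactly 7 days after Doses 3-6. The earliest patients are the likeliest to have had them. This is plausible and limits the practical effect. The documents do not date the change, though, and the current text still pairs the old review time with the new schedule.

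The Safety Committee's duties are set out in a Safety Analysis Plan (Protocol 9.8) that is not available here. It may require minimum data. If it does, the committee would have to depart from the 7-10 day clause, because Table 1 guarantees no collection in time.

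Other safeguards stand: 24-hour SAE reporting, ongoing AE collection and blinded review, each patient's own pre-dose liver check, the rule that suspends dosing after two related events across both cohorts, and the DMC. None puts sentinel labs or diaries before the committee at day 7-10. Scheduled DMC meetings (SAP 5.3.12) come after Day 85 of the first 20 patients and at the end, so none is tied to Doses 4-6.

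A reader might infer that later doses are riskier because the immune response rose with each dose. The documents do not show that. Protocol 1.3 reports no effect of number of doses on safety and no hepatitis flares, and 4.3 says vaccine reactogenicity typically appears within 3 days. Those safety data stop at three doses, so the risk at Doses 4-6 is unmeasured, not shown to be higher.

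**Conclusion.** The point holds as a timing mismatch in the current text: a release decision that one event can halt, and that rests mostly on labs and diaries, can be taken before all of them are in. The gap is nominally 18-21 days (at least 14) for Dose 3-6 diaries and Dose 6 labs in the last-dosed sentinel patients, and up to as long for Dose 3-5 labs. On assumed even accrual, 2-3 of 12 sentinel patients and about 2 expanded patients are affected.

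Two stronger readings are not supported. One is that Doses 3-6 are released without sentinel data: on even accrual 9-10 of 12 sentinel patients would be complete, and Dose 3-5 labs may be on time. The other is that patients were in fact dosed without these data, or harmed: no accrual pattern or amendment date is given, and the SAP Introduction reports that HepTcell was well tolerated with no significant safety events before termination for lack of efficacy. The review step is weakened, not void. The correction is worthwhile because it is cheap.

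**What to change.** For Doses 3-6, replace the fixed 7-10 day time with a review held once that dose's safety labs and 7-day diaries are available for all ongoing sentinel patients, and state that no expanded-cohort patient receives the dose before that review. For Doses 1-2, hold the review after the 7±2 day visit data are in. Make the change wherever the clause appears: the Protocol Study Summary, Protocol 4.1 and 6.4, and SAP 5.3.3.1 and 5.3.12. Add that a lab or diary documented as unobtainable is replaced by a repeat lab or an investigator interview, so that one lost record does not block release. As an editorial matter, align Protocol Appendix 1 and SAP 2.3, which still describe 7±2 day visits after every dose.

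In practice, start the expanded cohort about 28 days after the last sentinel patient's Dose 1, plus lab turnaround and up to 4 days for visit windows. Starting on sentinel Day 29 alone is not enough: expanded Dose 6 would fall on Day 29 + 140 = 169, the day the sentinel Dose 6 labs are drawn.

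**Cost.** Against a start on Day 8-11, the delay is 29 - 11 = 18 to 29 - 8 = 21 days, or 33 - 11 = 22 to 33 - 8 = 25 with the window margin. That is 18/730 = 2.5% to 25/730 = 3.4% of enrolment. Turnaround is not given; an assumed 4 days makes the upper end 29/730 = 4.0%. No visits are added. Screening must be timed so that waiting patients stay within 35 days. A sentinel visit delayed by illness could still hold a few expanded patients past their ±2 day dosing window.

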ALT or AST ≥ 10×ULN, and Total and direct bili < 1.5×ULN, and INR < 1.3 ×ULN	Interrupt dosing Monitor liver panel weekly If ALT/AST fall to <5×ULN, restart dosing; if ALT/AST fall to <1.5×, stop weekly monitoring	If the event does not resolve in 4 weeks or recurs, consult medical monitor about discontinuing study medication
ALT or AST \geq 5×ULN, and Total or direct bili \geq 1.5×ULN, or INR \geq 1.3 ×ULN		Discontinue study medication
ALT or AST $< 5 \times ULN$, and Total or direct bili $\ge 1.5 \times ULN$, or INR $\ge 1.3 \times ULN$	Interrupt dosing Monitor liver panel weekly If total and direct bili fall to <1.5 ×ULN and/or INR falls to < 1.3× on 2 consecutive tests, stop weekly monitoring and restart dosing	If the event does not resolve in 4 weeks or recurs, consult medical monitor about discontinuing study medication

For patients with Gilbert Syndrome, the 1.5 × ULN criteria for total and direct bilirubin will be replaced with a 1.5 × ULN for direct bilirubin and there will be no monitoring criteria for total bilirubin [Fontana 2020]. Other etiologies of ALT, AST, total and direct bilirubin, and INR elevations, such liver injury induced by other drugs and other viral infections, should be ruled out and treated accordingly.

If a patient prematurely discontinues study medication on or before Day 169, the Day 169/Early termination procedures will be performed. Patients who prematurely discontinue study medication will remain in the study for follow-on study assessments.

Patients will be followed for 52 weeks after the last dose of study medication (504 days beyond Day 1 for patients who complete the 24-week Treatment Period). AEs and concomitant medications will be recorded from the signing of informed consent to Day 169, but only MAEs, NCIs, and IMCs, which will be categorized as AEs, will be followed subsequently. Likewise, concomitant medications will be recorded through Day 169, but only immunosuppressive medications, vaccines, and new HBV treatments or medications associated with MAEs, NCIs, SAEs, hepatitis flares, or hepatic injury will be recorded beyond this point. At the end of the clinical trial, the decision about follow-on treatments and medical care will be made by the patient's medical physician or medical team in accordance with the usual standard of care.

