7.1.1. Stopping Rules

In consultation with the DMC, the following Stopping Rules will be applied:

- ALT or AST $\geq 10 \times ULN$
- INR ≥ 1.3
- Total bilirubin $\geq 1.5 \times \text{ULN}$ (excluding patients with Gilbert Syndrome)
- Direct bilirubin $\geq 1.5 \times \text{ULN}$ (for patients with Gilbert Syndrome)
- SAEs
- Severe systemic reactogenicity event (see Appendix 1)

If any of the Stopping Rules are met in one or more patients in the sentinel cohort (ie, the first 12 patients dosed) and the event(s) is deemed possibly or probably related to study medication, dosing will be suspended pending DMC review. Similar procedures will be

applied if 2 or more patients in the sentinel or expanded study cohort together experience Stopping Rules deemed possibly or probably related to study medication at any time during the 24-week Treatment Period. DMC recommendations may include instituting modifications to ensure the safety of continued dosing or discontinuing the study.

If the study is halted based on a DMC decision or safety concern, the trial will only be restarted after notification of the competent authority via a substantial amendment.

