9.1.2. Adverse Drug Reaction

All noxious and unintended responses to a medicinal product related to any dose should be considered an adverse drug reaction. A reaction means that a causal relationship between a medicinal product and an AE is at least a reasonable possibility, i.e., the relationship cannot be ruled out.

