9.1.3. Unexpected Adverse Drug Reaction

An unexpected adverse drug reaction is defined as an adverse reaction, the nature or severity of which is not consistent with the reference safety information in the Investigator's Brochure.

For the purpose of expedited reporting of unexpected serious adverse drug reactions (ie, Suspected Unexpected Serious Adverse Reactions [SUSARs]), only possibly or probably related and unexpected SAEs (Section 9.3.2) will be considered serious adverse drug reactions.

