9.3.2. Relatedness (Causality)

The assessment of causality will be based on the information available and may be changed upon receipt of additional information.

Causality should be assessed using the following categories:

- Unrelated/Unlikely Related: clinical event with an incompatible time relationship to investigational agent administration, and that could be explained by underlying disease or other drugs or chemicals or is incontrovertibly not related to the investigational agent
- Possibly related: clinical event with a reasonable time relationship to investigational agent administration, and that is unlikely to be attributed to concurrent disease or other drugs or chemicals
- Probably related: clinical event with plausible time relationship to investigational agent administration, and that cannot be explained by concurrent disease or other drugs or chemicals

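### The causality scale in Protocol 9.3.2 has no place for a well-timed event with a competing cause, so it permits a missed dosing hold or SUSAR and contradicts 9.1.2

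*Protocol*

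**What the plan says.** **The hold.** Protocol 4.1 (and the Study Summary) suspends dosing pending DMC review on a condition about relatedness to HepTcell: "If any of the Stopping Rules in Section 7.1.1 are met in one or more patients and the event(s) is deemed possibly or probably". Section 6.4 applies it when Stopping Rules "are met in one or more patients in the sentinel cohort and the event(s) is deemed possibly or probably related to HepTcell". Section 7.1.1 extends it across cohorts; the same steps are "applied if 2 or more patients in the sentinel or expanded study cohort together experience Stopping Rules deemed possibly or probably related".

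**SUSARs.** Section 9.1.3 uses the same categories and cites the scale by number: "only possibly or probably related and unexpected SAEs (Section 9.3.2) will be considered serious adverse drug reactions".

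**The scale (9.3.2).**
- *Possibly related* needs reasonable timing, "and that is unlikely to be attributed to concurrent disease or other drugs or chemicals".
- *Probably related* needs plausible timing and no possible explanation by such causes.
- *Unrelated/Unlikely Related* is a "clinical event with an incompatible time relationship to investigational agent administration, and that could be explained by underlying disease or other drugs or chemicals", or an event that is beyond dispute not related.

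**The general definition (9.1.2).** In a reaction, a causal link "is at least a reasonable possibility, i.e., the relationship cannot be ruled out".

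**The concern.** The hold protects patients other than the one who had the event, and it depends entirely on how relatedness is classified. HepTcell is meant to strengthen T cell immunity against HBV. Hepatitis flares are a named safety endpoint (3.4), and Section 4.3 says the monitoring is there partly to guard against them. Four of the six Stopping Rules in 7.1.1 are liver tests (ALT/AST, INR, total bilirubin, direct bilirubin), and every patient has chronic hepatitis B. A Stopping Rule event caused by the vaccine may therefore come with a ready alternative explanation.

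If the scale lets such an event fall outside both related categories, dosing of the other patients need not pause for DMC review, and a serious unexpected event need not be handled as a SUSAR. Two of the approximately 35 centers, one working from 9.1.2 and the other from 9.3.2, could classify the same event differently.

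**Working it through.** No arithmetic applies. The check is to cross the two attributes that 9.3.2 uses, timing and competing cause, and see which category each combination meets.

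1. **Timing fits, competing cause unlikely.** *Possibly related*: the hold applies.
2. **Timing fits, competing cause impossible.** *Probably related*: the hold applies.
3. **Timing does not fit, another explanation available.** *Unrelated/Unlikely Related*: no hold.
4. **Timing fits, competing cause credible.** Not *possibly related*, because a competing cause is not unlikely. Not *probably related*, because the event can be explained otherwise. Not *unrelated*, because the timing is compatible and nothing makes non-relation certain. No category fits, so the hold is not required.

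**Can case 4 occur here?** The protocol admits at least two competing causes and possibly a third.
- Steatosis is allowed at entry, with ALT and AST up to 1.5 × ULN (Inclusion Criterion 6).
- COVID-19 vaccination is allowed during dosing (6.7.1). It could be offered as the explanation for a severe systemic reactogenicity event, which is itself a Stopping Rule.
- HBV itself counts if *concurrent disease* is read to include it. Section 4.1 asks that other causes of liver abnormality, "such liver injury induced by other drugs and other viral infections, should be ruled out", but HBV is present in everyone and cannot be.

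**Set 9.3.2 beside 9.1.2.** In case 4 the product's role has not been ruled out, so under 9.1.2 the event is a reaction. Under 9.3.2 it is not even *possibly related*. Section 9.1.3 then takes the narrower scale for SUSARs.

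**Set 9.3.2 beside the SAP.** SAP 5.3.3.2 treats as treatment-related every event not classed as unrelated or unlikely. SAP 5.3.9.1 counts a missing relationship as *possibly related* in the frequency tables. The final tables therefore default to caution where the live trigger does not.

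**Size.** The documents give no rate for Stopping Rule events and no proportion with a competing cause. Any probability of a missed hold would rest on invented inputs, so none is given.

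**The case against.** Several points on the other side stand.

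- **Concurrent versus underlying disease.** In 9.3.2 only the unrelated category speaks of *underlying* disease; the two related categories speak of *concurrent* disease. Exclusion Criterion 7 refers to underlying liver disease not related to HBV, which suggests that HBV is the underlying disease here. On that reading HBV is not a competing cause, and a well-timed flare can be *possibly related*. The reading is tenable, but 9.3.2 does not define either term. Steatosis and COVID-19 vaccination remain. Steatosis is a weak explanation for a rise to 10 × ULN, given the entry cap.
- **Clinical judgment.** Patients enter with inactive disease, essentially normal transaminases and no flare in the prior 6 months. An investigator can reasonably judge that a large ALT rise soon after dosing is unlikely to be the natural course of HBV. This is why the wording permits a missed hold but does not force one.
- **No citation.** The hold sentences do not refer to 9.3.2. They say the event is deemed related, allow unblinding to assess this, and 7.1.1 adds consultation with the DMC. However, they use the category names of 9.3.2, and the protocol has no other scale. The Safety Analysis Plan and DMC charter were not available and might set another standard.
- **The continuation sentences.** Sections 4.1, 6.2 and 6.4 allow continuation if no Stopping Rule is met, with no relatedness condition. This is a real counterweight, but it leaves unaddressed the case where a rule is met and the event is judged unrelated.
- **Other safeguards.** The affected patient's dosing is interrupted or stopped regardless of causality (liver table in 4.1; 6.4). All SAEs go to the Sponsor within 24 hours whatever the relationship (9.7.2). The Safety Committee reviews all AEs, and the DMC may see unblinded data as needed.

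**Conclusion.** The text is wrong as written: 9.3.2 contradicts 9.1.2 and leaves a class of events without a category. The consequence is limited to the hold for other patients and to SUSAR classification, and it depends on how investigators resolve the gap.

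A reader might infer that a liver flare can never trigger the hold, or that its probability drops to zero. The documents do not support that. A case 4 event fails the unrelated category as well, and 9.7.2 demands a causality determination for every SAE, so its classification is undetermined. Nor do they show that *concurrent disease* includes HBV, or that the affected patient would keep receiving doses. An endpoint-level flare (ALT at least 3 × ULN and 100 U/L) is not itself a Stopping Rule, and a non-serious ALT rise is not a SUSAR under either definition.

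The conclusion assumes that the hold sentences use the terms as 9.3.2 defines them. SAP Section 2 reports that the study is being terminated for lack of efficacy, with no significant safety events. Rewording can therefore no longer change dosing here. The point bears on how recorded relatedness is read and on any reuse of this protocol text.

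**What to change.** In 9.3.2:
- Define *Possibly related* as a reasonable time relationship where a causal role cannot be ruled out, even if concurrent disease (including HBV) or another drug could also explain the event.
- Define *Unrelated/Unlikely Related* as no reasonable time relationship, or clearly due to another cause.

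In 7.1.1, add that attribution to HBV alone does not make a liver Stopping Rule event unrelated unless the unblinded DMC so decides.

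Leave the continuation sentences in 4.1, 6.2 and 6.4 as they stand. Tying them to related events would add a filter they do not now have and would loosen the safeguard. The Stopping Rule thresholds also stay unchanged.

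The cost is a rewording of one section and one added sentence, with no extra patients, visits or analyses. More events will be classed as related, so DMC reviews, temporary holds and SUSAR reports would rise somewhat.
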